### **4. Administration of Surveys and/or Process:**

Participants with a mobile phone listed in their medical record will be asked to complete the survey questions via text message. The questions will all be yes/no and asked in a sequence of text messages. Participants will be given the option to opt-out of participation, in addition to being provided with a phone number if they would prefer to answer the questions via telephone. Participants will be contacted via text message up to 2 times (approximately 1 week apart). Participants who do not decline further contact and do not respond to text message will be sent a recruitment letter via post, email, or portal as noted below.

Participants contacted via recruitment letter (email, patient portal, and/or post) will be asked to complete the survey using HIPAA-compliant REDCap, or by phone if preferred. The participants will be provided with a unique link to REDCap, whereby they will be asked to answer the survey questions. Patients will also be given a phone number to reach study team members if they would like to complete the survey on the phone, in addition to a mailing address if they prefer to answer the questions via mail (stamped return envelope included). Participants will be sent up to three reminders via email and given the option of opt-out of further contact by phone or email.

For recruitment letter and text message, the survey questions will be the same (described in Study Instruments).

### **5. Data Management:**

To ensure the privacy and confidentiality of clinical data, we will only store and use identifiable data on password-protected computers connected to the UPHS server. All study materials will be tracked with a unique participant ID and the study key will remain in a password-protected REDCap data form, accessible only by the PI and approved study staff. Data files will be kept in a secure area and destroyed according to UPenn IRB timelines.

The PI and select research staff will have access to these data. Computers connected to UPHS are highly secure and are required to comply with all HIPAA requirements. These computers are more secure than other computers at UPenn and thus will be the only ones where identifiable data are kept. Access to any participant data will be limited to the PI, Co-Is, and authorized study staff. All study team members will demonstrate completion of HIPAA training and will abide by the security procedures enforced at UPHS. All output containing individual identifiable information will be treated as confidential data. This information will never be transferred electronically via email or other pathways, never be included in analytic datasets, and will not be reported outside the study team.

## **7. Subject Follow-up:**

To explore impact of outreach, we will collect patient data in the EMR related to lung cancer screening and prevention (e.g., completed LCS, referral to tobacco cessation clinic) for up to 24 months after enrollment. All EMR data have been collected previously for non-research purposes (through clinical care) and thus, we are requesting a waiver of HIPAA authorization (see below).

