### **CHARACTERISTICS OF THE STUDY POPULATION:**

#### ***1. Target Population and Accrual:***

The target population includes primary care patients at Penn Medicine who are potentially eligible for LCS based on age (50-80 years old) or tobacco use (currently smoked or smoked within the last 15 years) but have never been screened for nor diagnosed with lung cancer. Currently, we cannot assess full LCS-eligibility of these patients because most (70% or greater) have no information regarding pack-years in their electronic medical record (EMR); thus, limiting our ability to assess true uptake of LCS in eligible patients and missing an opportunity

to reduce lung cancer mortality in our patients. Given the population health focus, we aim to include all patients who meet study eligibility at Penn Medicine, which we estimate will be approximately 6,125 patients across the study timeline. Patients will accrue as identified in the electronic health record (EHR) throughout the study duration and contacted in batches to monitor enrollment response and address any unintended negative impacts on patients or providers that may arise.

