## **STUDY DESIGN:**

We will use a phased, cross-sectional approach to collect patient-reported information related to lifetime smoking history. We will assess correlation between self-reported data with smoking data (i.e., pack-years) in the subset of patients with pack-years documented in their EHR. The overall goal of this study is to develop scalable strategies for increasing identification of patients who meet 20 pack-year eligibility for LCS. The questions used in this study have been pilot tested with a smaller group of 303 patients and shown high positive predictive value (90.5%). We are now seeking to expand upon these results and apply to a larger group of patients to assess population-level reliability and eligibility assessment for LCS (Objective 1). In addition to advancing the development of a screening eligibility tool that can be applied across healthcare systems, we will use the results of the study to identify participants for future intervention trials seeking to improve LCS at Penn Medicine.

The duration of the study will be approximately 2 years, which will give sufficient time to collect patient-reported data and analyze reliability in relationship to medical record data. The research will be conducted in the Department of Family Medicine & Community Health and include all patients that meet eligibility criteria. The data collection and analysis will be conducted by trained clinical coordinators and data analysts within the PI's team that have experience with clinical trials in this context at Penn. The expected duration of active subject participation is less than 30 minutes (likely 5-10 minutes).

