## **STUDY PROCEDURES:**

### **1. Detailed Description:**

Potential participants will be identified using EMR data as noted above. We will first assess available contact information (i.e., email, mobile phone, and patient portal use) to identify if the patients will first be contacted via text message (if mobile phone listed in EMR), email (if email or patient portal use listed in the EMR), or post (if no mobile or email is listed in EMR). Then we will follow recruitment and administration of survey processes as noted above. All follow-up data will be collected using EMR data for up to 24 months.

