### **5. Statistical Analysis:**

We will summarize data using descriptive statistics to assess recruitment response by age, race/ethnicity, and other key patient demographics (Objective 1). For patients who complete the screening tool and who have pack-year information documented in their medical record (anticipate ~20-30% based on prior work), we will explore the reliability of the screening tool (i.e., survey questions) to predict 20 pack-year eligibility for LCS. We will calculate the positive and negative predictive value, sensitivity, and specificity of the screening tool overall and by race, sex, and age group to assess equity. As exploratory analyses, we will use descriptive statistics and logistic regression to evaluate overall uptake of LCS in patients who complete the screening tool and assess relationships between patient characteristics (e.g., age, sex, race), smoking history, and LCS completion. For Objective 2, we have outlined our statistical analysis (see attached).

The long-term objective of this study is to increase pack-year eligibility at the population level and thus we will include all patients who meet age eligibility for LCS. Additionally, prior studies have indicated that survey response rates using are likely to be <30%, and thus including a large sample of patients will enable us adequate sample to assess reliability of the screening tool overall and within important subgroups (e.g., females and Black adults) where there are concerns regarding LCS uptake inequities.

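### The exploratory logistic regression of LCS uptake has no common time window or data cut, so follow-up may be unequal and the uptake figure hard to interpret

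*Protocol*

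**What the plan says.** Four parts of the protocol bear on this.

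- **Accrual** (Characteristics of the Study Population, 1. Target Population and Accrual): "Patients will accrue as identified in the electronic health record (EHR) throughout the study duration and contacted in batches".
- **Length of study** (Study Design): "The duration of the study will be approximately 2 years".
- **Follow-up** (Methods, 7. Subject Follow-up): LCS and related data are taken from the medical record "for up to 24 months after enrollment". Study Procedures, 1. Detailed Description, repeats it: "All follow-up data will be collected using EMR data for up to 24 months". Both give a maximum and neither gives a minimum.
- **Analysis** (Study Procedures, 5. Statistical Analysis): "we will use descriptive statistics and logistic regression to evaluate overall uptake of LCS in patients who complete the screening tool", and the model is to "assess relationships between patient characteristics (e.g., age, sex, race), smoking history, and LCS completion". The analysis is labelled exploratory.

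No section sets an uptake window, a data cut for this analysis, a censoring rule, or an adjustment for entry date or length of follow-up. The SAP does not fill the gap. Its section 5d sets explicit windows for survey response (days 0 to 7 and 8 to 60), but it does not cover LCS uptake.

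**The concern.** A logistic model of a yes/no outcome gives the same weight to a patient observed for 3 months and to one observed for 24. If both kinds of patient are in the data, two things can go wrong.

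First, the overall uptake percentage belongs to no stated time horizon. It mixes follow-up lengths, falls below 24-month uptake, and cannot be compared with a rate from another setting or a later trial.

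Second, entry date becomes a strong predictor of completion because early entrants had longer to be screened. A characteristic that differs between early and late batches could then appear related to LCS completion when it is not. Age, sex and race are the named predictors, and the study's interest in equity makes a spurious association with any of them unwelcome.

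**Working it through.** **Is there a figure to reproduce?** No. The documents give no expected uptake, precision or power for this analysis. What follows is an illustration on stated assumptions.

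**Inputs from the protocol.** Maximum follow-up is 24 months, the study lasts about 24 months, and entry is rolling and in batches.

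**Assumptions.**
- The screening rate is constant.
- Entry is uniform over the first *A* months.
- Extraction stops at month 24.
- True 24-month uptake *U* is 5%, 10% or 20%. The Background section cites about 5% national completion, but that is not a 24-month figure for this cohort, so a range is used.

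**Step 1: crude uptake.** The monthly rate is λ = −ln(1 − U)/24. A patient followed for *t* months is screened with probability f(t) = 1 − exp(−λt). Averaging over entry gives

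crude uptake = 1 − [exp(−λ(24 − A)) − exp(−24λ)] / (λA).

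For U = 10%, 24λ = 0.10536. With A = 24 this is 1 − (1 − 0.9)/0.10536 = 0.0509.

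| Entry spread over | Mean follow-up | U = 5% | U = 10% | U = 20% | Crude ÷ U |
|---|---|---|---|---|---|
| 0 months | 24 months | 5.00% | 10.00% | 20.00% | 1.00 |
| 6 months | 21 months | 4.39% | 8.80% | 17.73% | 0.88–0.89 |
| 12 months | 18 months | 3.77% | 7.59% | 15.37% | 0.75–0.77 |
| 18 months | 15 months | 3.15% | 6.35% | 12.92% | 0.63–0.65 |
| 24 months | 12 months | 2.52% | 5.09% | 10.37% | 0.50–0.52 |

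The first row also describes extraction that continues until everyone has 24 months: the shortfall is then nil, whatever the accrual pattern.

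**Step 2: entry date as a predictor.** For U = 10%, entry at month 0 gives f(24) = 0.100 and entry at month 12 gives f(12) = 0.0513. The odds ratio is (0.100/0.900)/(0.0513/0.9487) = 2.05 with no true difference. Across the three values of U it is 2.0 to 2.1, and for month 0 against month 18 it is 4.1 to 4.4.

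**Step 3: carry-over to a patient characteristic.** Take 24-month accrual and U = 10%. Mean uptake is 0.0759 for entrants in the first 12 months and 0.0259 for entrants in the last 12. Suppose 60% of one group and 40% of the other entered early:

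- group 1: 0.6 × 0.0759 + 0.4 × 0.0259 = 0.0559
- group 2: 0.4 × 0.0759 + 0.6 × 0.0259 = 0.0459
- odds ratio: (0.0559/0.9441)/(0.0459/0.9541) = 1.23

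Across the three values of U, a 60/40 split gives 1.23 to 1.24, a 70/30 split gives 1.51 to 1.55, and an even split gives 1.00.

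**Step 4: after the fix.** With a fixed 12-month window every patient has the same target, f(12): 2.5%, 5.1% and 10.6% for the three values of U, whatever the entry date.

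**The case against.** The strongest reply is that the unequal follow-up rests on a data cut the protocol never states. Study Design justifies the 2 years by survey collection and the comparison with medical record data, and does not mention LCS follow-up. Subject Follow-up counts time per patient from enrollment and uses routine records that need no patient contact. Extraction could therefore run on after accrual ends; with 24 months of accrual, until month 24 + 24 = 48. Every patient would then have the full period and the problem would disappear. This stands, and it makes the bias conditional.

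The halving is also the extreme case. Study Procedures, 2. Data Collection, says age-eligible patients were already identified under an existing protocol, so entry may be front-loaded and the loss smaller. This stands too.

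A reader might infer more: that the plan does understate uptake by half, that its covariate associations are confounded, or that logistic regression is the wrong model. The documents support none of these. *Understated* needs a target, and the protocol names only overall uptake; in the 24-month row, the crude figures are close to 12-month uptake. No section says batches are ordered by age, sex, race or smoking history. Logistic regression is sound once the outcome has a fixed, fully observed window.

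Finally, the label "As exploratory analyses, we will use descriptive statistics and logistic regression" sets the weight of the point. LCS uptake is not in either numbered objective and is not an SAP endpoint.

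What the reply does not supply is the missing rule. On either reading, the protocol has to say when extraction ends and over what period uptake is counted.

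**Conclusion.** The concern holds in conditional form. The protocol combines rolling entry, a maximum but no minimum follow-up, and a binary model, and states no common window or data cut. Unless extraction continues until every patient has 24 months, follow-up will be unequal and crude uptake will fall below 24-month uptake. On the assumptions above (constant rate, cut at month 24), it would be about 0.88 of it for 6-month accrual, 0.76 for 12-month and 0.5 for uniform 24-month accrual. Spurious associations are possible but not shown, since they need a characteristic related to entry date.

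This is a worthwhile, inexpensive improvement to an exploratory analysis. It has no bearing on the 7-day survey endpoint, the comparison of message and incentive arms, or the sensitivity, specificity and predictive values of the tool.

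**What to change.** In the protocol's Statistical Analysis section, state the date on which extraction for LCS uptake ends and the day from which time is counted. Then choose one of two routes.

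1. **Time to event.** Report LCS completion as Kaplan-Meier cumulative incidence at fixed times from the index date (for example 6 and 12 months), and model it with Cox regression censored at the data cut. This keeps every patient.
2. **Fixed window.** Keep logistic regression, with the outcome defined as completion within, say, 12 months, among patients whose enrollment date allows the full window. Eligibility must depend on enrollment date alone; admitting late entrants because they were screened early would bias uptake upwards.

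With either route, adjusting for batch or entry date would guard against differences between early and late entrants.

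The cost is a sentence or two. Risk/Benefit Assessment, 5. Protected Health Information, already obtains dates and converts them to time from an index date. Time from index date to data cut should be derived in the same step, before identifiers are removed. The fixed-window route loses late entrants: with uniform 24-month accrual, a month-24 cut and a 12-month window, 12/24 = half of patients; with accrual of 12 months or less, none.

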## **STUDY PROCEDURES:**

### **1. Detailed Description:**

Potential participants will be identified using EMR data as noted above. We will first assess available contact information (i.e., email, mobile phone, and patient portal use) to identify if the patients will first be contacted via text message (if mobile phone listed in EMR), email (if email or patient portal use listed in the EMR), or post (if no mobile or email is listed in EMR). Then we will follow recruitment and administration of survey processes as noted above. All follow-up data will be collected using EMR data for up to 24 months.

### **2. Data Collection:**

As part of our existing IRB-approved study (Protocol #830184), we have identified patients at Penn who meet age eligibility for LCS and extracted retrospective PHI and clinical data needed for this study. Thus, this study will not require retrospective extraction of data. However, we are requesting that data for prospective identification of new patients (2023-2025) and their clinical data (e.g., smoking data, LCS uptake) be collected as part of this protocol. We will use similar methods including data management and safety protocol as have been used successfully in this prior protocol. Patient-reported data (i.e., screening eligibility tool) will be collected using text message or secure survey platforms (i.e., REDCap).

### **3. Genetic Testing:**

Not applicable

### **4. Use of Deception:**

Not applicable

### **5. Statistical Analysis:**

We will summarize data using descriptive statistics to assess recruitment response by age, race/ethnicity, and other key patient demographics (Objective 1). For patients who complete the screening tool and who have pack-year information documented in their medical record (anticipate ~20-30% based on prior work), we will explore the reliability of the screening tool (i.e., survey questions) to predict 20 pack-year eligibility for LCS. We will calculate the positive and negative predictive value, sensitivity, and specificity of the screening tool overall and by race, sex, and age group to assess equity. As exploratory analyses, we will use descriptive statistics and logistic regression to evaluate overall uptake of LCS in patients who complete the screening tool and assess relationships between patient characteristics (e.g., age, sex, race), smoking history, and LCS completion. For Objective 2, we have outlined our statistical analysis (see attached).

The long-term objective of this study is to increase pack-year eligibility at the population level and thus we will include all patients who meet age eligibility for LCS. Additionally, prior studies have indicated that survey response rates using are likely to be <30%, and thus including a large sample of patients will enable us adequate sample to assess reliability of the screening tool overall and within important subgroups (e.g., females and Black adults) where there are concerns regarding LCS uptake inequities.

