### **BACKGROUND:**

A growing body of evidence indicates that lung cancer screening (LCS) for high-risk adults reduces lung-cancer mortality by 16-20%. Despite this evidence, uptake of LCS in the United States remains suboptimal (~5% national completion rate in screening-eligible adults). Additionally, there are disparities in uptake by race, sex, and other key social determinants of health, reflective of the challenges of implementing LCS equitably.

LCS differs from other types of population-level cancer screening because eligibility assessment requires evaluation of lifetime smoking intensity, calculated by multiplying the average number of packs of cigarettes smoked per day by total years a person smoked (i.e., pack-years). While tobacco use (i.e., current, former, never) is well captured in electronic medical records (EMR), pack-years is often missing, highlighting the need for interventions focused specifically on this component of LCS-eligibility assessment. Prior approaches to assessing pack-years have used open-ended questions, which in comparison to other question formats (e.g., yes/no) is associated with increased respondent burden and lower response rates. As such, we seek to develop and test the feasibility and reliability of using brief yes/no questions (“simplified eligibility tool”) for predicting 20+ pack-year eligibility for LCS. This approach has shown high positive predictive value (90.5%) in our pilot study with 303 patients, and we are now looking to test the approach in a larger and more diverse sample of adult patients at Penn Medicine. This work will also help to support future pragmatic studies aiming to test strategies to increase lung cancer screening in eligible adults.

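### All four accuracy measures come only from completers with charted pack-years, and the plan neither states nor checks the assumption this needs

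*Protocol*

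**What the plan says.** Protocol, Study Procedures, 5. Statistical Analysis, limits the accuracy analysis to patients who complete the tool and "who have pack-year information documented in their medical record (anticipate ~20-30% based on prior work". In that group it plans the "positive and negative predictive value, sensitivity, and specificity of the screening tool overall and by race, sex, and age group", the breakdown being meant to assess equity. The Study Design section confirms that self-report is compared with the record only "in the subset of patients with pack-years documented in their EHR". Target Population and Accrual says that "most (70% or greater) have no information regarding pack-years" in the record.

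Neither document mentions weighting, imputation, a comparison of charted with uncharted completers, or a sensitivity analysis for missing pack-years. The SAP covers only the messaging and incentive experiment, and its Missing Data section deals with race, sex and survey completion. The Introduction and Purpose section makes reliability of the tool part of the study's primary purpose.

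**The concern.** The reference standard is present for a minority, and that minority is selected by routine charting rather than at random. The tool is intended for patients whose pack-years are not charted, yet every accuracy figure will come from those whose pack-years are.

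The Key Inclusion Criteria require age and a primary care visit but no smoking history, and the SAP's baseline table (section 8d) lists never-use as a tobacco status. Never-smokers can therefore be among the completers. If they seldom have pack-years entered, charting will differ by tobacco status and hence by tool result.

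At stake are the figures that would be carried into later trials and shared with other health systems, and the equity comparison. If charting relates to tool result or eligibility differently in two subgroups, equal accuracy can look unequal.

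**Working it through.** **Figures in the plan.** There is no sample size, precision target or expected sensitivity, specificity or NPV to reproduce. If 70% or more lack pack-years, at most 1 − 0.70 = 30% have them, which agrees with the upper end of 20-30%; the lower end cannot be derived. At most 6,125 × 0.30 = 1,838 patients complete the tool (the Protocol expects response below 30%), of whom 20-30% is 368-551 verified. At the SAP's hypothesized 3-12% of 6,000 (text phase, seven days) there are 180-720 completers and 36-216 verified.

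**Illustration 1 (all inputs assumed).** Sensitivity 0.80, specificity 0.85, prevalence 0.30. As shares of completers: TP 0.24, FN 0.06, FP 0.105, TN 0.595. Each cell is multiplied by its charting fraction and the raw rates are recomputed.

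| Charting pattern | Charted overall | Sens | Spec | PPV | NPV |
|---|---|---|---|---|---|
| Unrelated to tool result and eligibility (truth) | any | 80.0% | 85.0% | 69.6% | 90.8% |
| Tool-positive 35%, tool-negative 20% | 25.2% | 87.5% | 76.4% | 69.6% | 90.8% |
| Tool-positive 40%, tool-negative 15% | 23.6% | 91.4% | 68.0% | 69.6% | 90.8% |
| Never-smokers (40% of completers, all tool-negative) 10%, others 35% | 25.0% | 80.0% | 74.7% | 69.6% | 83.8% |
| Truly eligible 35%, not eligible 20% | 24.5% | 80.0% | 85.0% | 80.0% | 85.0% |

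- Row 2: sensitivity = 0.24×0.35 / (0.24×0.35 + 0.06×0.20) = 0.084/0.096; specificity = 0.595×0.20 / (0.595×0.20 + 0.105×0.35) = 0.119/0.15575.
- Row 4: charted TN = 0.40×0.10 + 0.195×0.35 = 0.10825; charted FP = 0.105×0.35 = 0.03675; specificity = 0.10825/0.145. Charted FN = 0.06×0.35 = 0.021; NPV = 0.10825/0.12925.
- Row 5: PPV = 0.24×0.35 / (0.24×0.35 + 0.105×0.20) = 0.084/0.105; NPV = 0.595×0.20 / (0.595×0.20 + 0.06×0.35) = 0.119/0.140.

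**What a correction does.** In row 4, weighting by tobacco status restores TN = 0.04/0.10 + 0.06825/0.35 = 0.595 and FP = 0.03675/0.35 = 0.105, so specificity returns to 85.0%. In row 5, Begg-Greenes on tool result alone (tool-positive share 0.345) gives sensitivity 0.345×0.80 / (0.345×0.80 + 0.655×0.15) = 0.276/0.37425 = 73.7% and specificity 0.55675/0.62575 = 89.0%. The correction then moves two correct raw values away from the truth.

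**Illustration 2 (tied to the pilot PPV).** PPV 0.905 is the Protocol's; tool-positive share 0.30 and NPV 0.90 are assumed. TP 0.2715, FP 0.0285, FN 0.07, TN 0.63. With k the ratio of charting in tool-positives to tool-negatives, raw sensitivity = k·TP/(k·TP + FN) and raw specificity = TN/(TN + k·FP). The overall charting level cancels.

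| k | Raw sens | Raw spec |
|---|---|---|
| 0.5 | 66.0% | 97.8% |
| 1 (no bias) | 79.5% | 95.7% |
| 1.5 | 85.3% | 93.6% |
| 2 | 88.6% | 91.7% |
| 3 | 92.1% | 88.1% |

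For tool-positive shares of 0.2-0.4 and NPV of 0.85-0.95, k = 2 puts raw sensitivity about 4 to 15 points too high and specificity about 2 to 6 points too low. If instead eligible patients are charted twice as often as others, raw sensitivity and specificity are right, PPV reads 95.0% and NPV 81.8%, and Begg-Greenes sensitivity is 69.1% against a true 79.5%.

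**Subgroups.** Suppose the tool performs identically in two groups, but one follows row 1 and the other row 2. The raw figures differ by 7.5 points in sensitivity (87.5 − 80.0) and 8.6 in specificity (85.0 − 76.4) with no true difference. A difference in charting level alone, with no link to tool result or eligibility within each group, would not do this.

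**The case against.** The strongest reply is that charting happens in routine care (Protocol, Subject Follow-up), and nothing in the documents says the tool prompts it. If heavier smokers are charted more often, charting depends on true smoking intensity. Raw sensitivity and specificity are then correct, and a correction on tool result alone makes them worse. This stands, and it rules out simply replacing the raw rates with Begg-Greenes estimates.

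It is also fair that every charting rate above is assumed. The first illustration implies a PPV of 69.6%, where the Protocol says "This approach has shown high positive predictive value (90.5%) in our pilot study with 303 patients"; tied to that figure, the specificity shift is smaller. The measure the Protocol cites is PPV, which is unbiased if charting depends only on tool result. The analysis is worded as exploring reliability. The verified sample is thin: tool result by three tobacco levels by two levels each of age, race and sex makes 48 cells, for 36 to 551 verified patients. Finally, the tool result is not available for every responder, since some answer only in part and some answers may be coded unknown.

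These points limit the claim but do not remove it. The plan reports all four measures, and each non-random pattern in the first table distorts at least two of them. Tobacco status, according to the Protocol's Background, is well captured, so the never-smoker route can be examined and corrected with data already held.

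**Conclusion.** The point holds as a cheap improvement. The plan presents verified-subset rates as the tool's accuracy, overall and by subgroup, without stating or checking the condition under which all four are valid together.

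A reader might infer that raw sensitivity will be overstated and specificity understated, by the 7 to 17 points in rows 2 and 3 of the first table. The documents do not support that. They do not say how charting relates to tool result or eligibility, and the same overall charting share is compatible with no bias, with bias in either direction, or with bias confined to PPV and NPV. The figures show only that the bias could be large enough to matter under plausible but assumed charting rates. That never-smokers are seldom charted is likewise an assumption, though one the study's own data can test.

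**What to change.** In Protocol section 5, Statistical Analysis:

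1. Compare charted with uncharted completers by tool result, tobacco status, age, race and sex.
2. Beside the raw rates, report all four measures over all completers with classifiable tool answers. Use inverse-probability-of-verification weights from a parsimonious model of tool result, tobacco status, age, race and sex, or Begg-Greenes within tool result by tobacco status, with bootstrap confidence intervals.
3. State that this assumes charting is ignorable given those variables, and add a sensitivity analysis in which charting also depends on true pack-year status.
4. Do not read raw subgroup differences as differences in tool accuracy where charting differs by subgroup.

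The cost is a paragraph of text and modest analysis time. Tool answers are recorded and the SAP's section 8d already lists the covariates, so no new data are needed. Confidence intervals will be wider, especially in subgroups given the small verified sample. The weighted estimates also rest on an assumption that the data cannot test, which is why the raw rates and the sensitivity analysis should stand beside them.
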